#### 10.4.10 TABULATION OF INDIVIDUAL RESPONSE DATA

An overall list of each subject with his or her CNC word score and AzBio sentence score at baseline, 1 month, 3 months, 6 months, and 12 months along with the change in CNC word score and AzBio sentence score from baseline to 6 months, will be provided.

# 10.4.11 EXPLORATORY ANALYSES

Exploratory analyses in the form of a repeated measures analysis will be done for the primary, secondary, and subjective questionnaire scores to characterize any changes over time.

#### 10.5 SAMPLE SIZE

The sample size estimate is based on attaining adequate power to test the co-primary endpoint of the study. The hypothesis test is a paired one-sample T-test of superiority of the mean change in CNC word score from baseline to 6-months with a superiority margin of 10 percentage points. The test will be performed at the one-sided alpha = 0.025 level. A sample size of 50 would yield approximately 90% power assuming the true change in mean CNC word score is 24.4 with a standard deviation of 21.9.

The paired T-test will also be used to test for superiority of the mean change in AzBio sentence score from baseline to 6-months with a superiority margin of 10 percentage points. The test will be performed at the one-sided alpha = 0.025 level. A sample size of 50 would yield approximately 83% power assuming the true change in mean AzBio sentence score is 15 with a standard deviation of 8.4.

The estimates used for the sample size calculation came from the results for the Electric-Acoustic System (EAS) Investigational pivotal trial.

#### 10.6 SAMPLE STRATIFICATION

In order to ensure that subjects enrolled in the study fill the entire range of candidacy scores from 0 to 60% correct on CNC words, minimum sample sizes of 10 subjects will be established across the following ranges: 0 to 20%, 21 to 40%, and 41 to 60% correct.

# 10.7 MEASURES TO MINIMIZE BIAS

Because this is a one-arm trial with all subjects receiving the same treatment, measures to minimize bias in the form of randomization and blinding are not relevant. However, one form of bias control implemented in this trial is that the presentation order of the CNC word lists is randomized at each follow up visit.

## 10.8 SITE POOLABILITY

Poolability across site of the data used for analysis of the primary endpoint will be established. For each subject, the change from baseline to 6 months in CNC word score and AzBio sentence score will be computed. The changes in CNC word score and AzBio sentence score will be analyzed using a one-way analysis of variance in which site forms the levels of the single factor. The overall F-test will be used to demonstrate poolability of the primary endpoint data. If the p-value for the overall F-test is greater than or equal to 0.10 then the data will be considered

poolable. If the p-value is less than 0.10, then additional methods may need to be employed in the analysis of the primary endpoint. These methods will be detailed in the SAP.

#### 10.9 PROPENSITY SCORE ANALYSIS

The primary endpoints of this trial were also measured in the Electric-Acoustic Stimulation clinical trial. The results from the current study will be compared back to the EAS pivotal trial via use of a propensity score analysis. Propensity scores for the subjects in each trial will be generated using a logistic regression which estimates the probability that a subject was treated in the current or previous study. The baseline variables used to generate the propensity score are age, sex, CNC word score, and low-frequency hearing loss. Combining the propensity scores from both trials, five strata will be formed using the quintiles of the scores. The analysis of CNC word score will be done using generalized linear models. Differences from baseline in the CNC scores will be the dependent variable while study (a coded value) and the propensity quintile will act as the independent predictors. Use of the quintile in the model adjusts the estimates of treatment effect for the propensity score.

A propensity score analysis of this type requires that there is good overlap of the propensity scores from the original EAS pivotal trial and the current expanded indications trial. In the absence of good overlap, estimate of the treatment effect can still be made, but may be severely biased.

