In addition to considering the use of more difficult test materials to expand criteria on speech understanding measures, candidates with more low-frequency residual hearing are also being implanted. Verschuur and colleagues (2016) reported a significantly greater proportion of referred candidates with low frequency thresholds better than 80 dB HL between the years of 2011-2015, compared to referred candidates between 1990-2010. With the approval of the MED-EL EAS System, individuals with normal hearing to moderate hearing loss in the low frequencies qualify for cochlear implantation. The benefits of EAS have been reported by several research groups (Gantz, Turner, & Gfeller, 2006)(Dorman, Gifford, Spahr, & McKarns, 2007)(Von Ilberg, Baumann, Kiefer, Tillein, & Adunka, 2011)(Gifford et al., 2013). For example, Dorman demonstrated substantial improvement in performance on words in guiet and sentences in noise when adding low-frequency acoustic information ipsilaterally for 15 subjects with cochlear implants. In addition, Gifford, et.al (2007) also reported on individuals with residual lowfrequency hearing and the use of a contralateral hearing aid (bimodal stimulation). For the 11 subjects included in this study, performance on CNC words was statistically better in the bimodal condition as compared to the cochlear implant alone. Ten of the 11 subjects preferred to wear the contralateral hearing aid for the majority of waking hours.

The results from a recent international survey on candidacy guidelines around the world were provided by Vickers and colleagues (2016). Results included responses from 28 individuals, representing 17 countries. Audiometric guidelines for adult cochlear implantation are present in 70% of the countries surveyed, with more emphasis on thresholds in the high frequencies as opposed to low-frequency residual hearing. Of the respondents, 85% of the countries surveyed have speech-based criteria in place for adult CI candidates. Of those countries, 40% use tests of word understanding and an additional 36% use both word and sentence understanding as part of the criteria. Tests of speech understanding using monosyllabic words can be easier to compare across languages, making evaluations of CI performance across the globe possible.

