#### 5 STUDY ENROLLMENT AND WITHDRAWAL

#### 5.1 PARTICIPANT INCLUSION CRITERIA

Individuals must meet all of the inclusion criteria set forth below in order to qualify for inclusion in this study.

- Adults, 18 years of age or older at the time of implantation
- Moderate to profound hearing loss in the low frequencies and severe to profound hearing loss in the high frequencies, bilaterally as defined by (see *Figure 1* below for example audiogram information)
  - o Low-frequency PTA (250, 500, and 1000 Hz) greater than 40 dB
  - High-frequencies not better than 65 dB (3000 Hz 8000 Hz)
- Sensorineural hearing loss, demonstrated by an air-bone gap of less than or equal to 10 dB
- Limited benefit from appropriately fit hearing aids, defined by CNC word score in quiet of 60% or less in the ear to be implanted and 70% or less in the non-implanted ear
- CNC word score in quiet of greater than or equal to 10% in the ear to be implanted
- Evidence of appropriately fit hearing aids as determined by the audiologist
  - Bilateral hearing aids should be considered standard of care, except in situations where the audiologist, physician, or potential subject determines that unilateral fit is optimal

- Hearing aid fit should be verified through accepted measures such as functional gain or real-ear verification
- If appropriately fit hearing aids have not been worn within the last year, a 30day hearing aid trial must be completed prior to enrollment in the study
- Fluent in English
- No radiological contraindications
- Ability to undergo general anesthesia
- Appropriate motivation and expectation levels
- Stated willingness to comply with all study procedures for the duration of the study

[figure not shown]

FIGURE 1 – Example inclusion audiogram showing audiometric threshold criteria. NOTE: Subjects may fall outside of the shaded area but still meet the PTA criteria.

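### Section 10.9 adjusts the CNC comparison with the EAS trial only through five propensity strata; adding baseline CNC, and low-frequency PTA where overlap allows, would cheaply reduce a probably modest residual bias.

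*Combined protocol and SAP*

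**What the plan says.** Section 10.9 sets the current results against the EAS pivotal trial. A logistic model gives each subject a score for belonging to one trial or the other: "The baseline variables used to generate the propensity score are age, sex, CNC word score, and low-frequency hearing loss". The scores are pooled and "five strata will be formed using the quintiles of the scores". For the outcome model, "Differences from baseline in the CNC scores will be the dependent variable", and "study (a coded value) and the propensity quintile will act as the independent predictors". No other covariate is listed, and the text does not say whether the quintile enters as a class or as a number.

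The section states that good overlap is needed and adds: "In the absence of good overlap, estimate of the treatment effect can still be made, but may be severely biased". It names no overlap or balance check and no fallback.

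Two other places bear on overlap. Section 2.1 says of the approved EAS system that "individuals with normal hearing to moderate hearing loss in the low frequencies qualify for cochlear implantation". Section 5.1 requires, for this trial, "Low-frequency PTA (250, 500, and 1000 Hz) greater than 40 dB", with limited benefit "defined by CNC word score in quiet of 60% or less in the ear to be implanted" and at least 10% in that ear.

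**The concern.** Two baseline variables probably remain out of balance within strata. Baseline CNC is subtracted to form the outcome, so subjects who start low tend to gain more. Low-frequency hearing probably differs between the trials, so the score may separate them strongly, and a fifth of the pooled sample can then span a wide range of hearing. Any such imbalance goes into the study coefficient and could be read as a difference in benefit between the new candidates and the earlier cohort.

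This is the only planned comparison with another implanted cohort, and the revision history says it was added on the regulator's recommendation, so it will be read. Both baseline values are already collected and already enter the propensity model. Using them again in the outcome model needs no new data.

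**Working it through.** Section 10.9 gives no sample size, power or bias figure, so there is none to reproduce.

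**Inputs from the documents.** Current trial: N = 50, low-frequency PTA above 40 dB, baseline CNC 10 to 60%. SD of CNC change: 21.9 (section 10.5, taken from the EAS trial). Not given: the EAS trial's N, entry rules and baseline values, and how CNC change depends on baseline values. All of these are assumed below.

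**Mechanism.** Let Y = CNC at 6 months − CNC at baseline, S = 1 for the current trial, and let quintile enter as a class. If Y depends linearly on baseline CNC (slope β1) and low-frequency PTA (slope β2), the planned coefficient has expectation

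δ + β1·D1 + β2·D2,

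where D1 and D2 are the average within-quintile differences (current minus EAS), weighted by n1·n0/(n1+n0). A quintile holding one trial has weight zero. Since Y subtracts baseline, β1 = (slope of 6-month on baseline score) − 1; assumed slopes of 0.2 to 0.6 give β1 = −0.8 to −0.4. For illustration, a residual imbalance of 3 CNC points gives 3 × 0.4 = 1.2 to 3 × 0.8 = 2.4 points of spurious difference.

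**Sampling error for scale.** With no adjustment and an assumed EAS N of 75: 21.9 × √(1/50 + 1/75) = 21.9 × 0.183 = 4.0 points.

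**Simulation 1** (1,500 runs per scenario, true study effect 0). Assumed: EAS N = 73; slopes −8 points per SD of baseline CNC and −5 per SD of low-frequency PTA; residual SD 18, so total SD √(64 + 25 + 324) = 20.3. The last column of estimates adds all four baseline covariates to study and quintile.

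| Assumed shift between trials | Study only | Planned: study + quintile | + covariates | SD, planned | Quintiles with one trial (of 5) |
|---|---|---|---|---|---|
| Low-frequency 0.5 SD | −2.63 | −0.28 | −0.05 | 3.5 | 0.00 |
| Low-frequency 1 SD | −5.00 | −0.44 | 0.05 | 3.8 | 0.04 |
| Low-frequency 2 SD | −9.83 | −0.59 | 0.21 | 5.1 | 1.10 |
| Low-frequency 1.5 SD, CNC 0.5 SD | −11.74 | −1.11 | −0.22 | 4.4 | 0.44 |
| Low-frequency 2 SD, curved effect | −18.05 | −1.65 | −0.16 | 5.2 | 1.10 |
| Ranges 15–65 dB (EAS) vs 40–90 dB | −8.46 | −0.79 | −0.23 | 4.7 | 1.41 |
| Low-frequency 2 SD, no effect on change | 0.12 | 0.03 | 0.04 | 4.9 | 1.14 |

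Monte Carlo error is about 0.1. Where there is raw bias, the planned model leaves a small share of it, for example 0.59/9.83 = 6% and 1.65/18.05 = 9%. Over all such scenarios run, including EAS N of 50 and 100, the share was 6 to 13% and the planned SD 3.2 to 5.7. In the curved row, root mean square error goes from √(1.65² + 5.2²) = 5.46 to √(0.16² + 5.1²) = 5.10, about 6.5% lower.

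**Simulation 2** (400–500 runs per scenario, sharper separation). Assumed: EAS N 50 or 75; EAS low-frequency PTA 10 to 50 or 60 dB against 41 to 80–100 dB here; EAS CNC 0 to 40 or 60 against 10 to 60 here; β1 = −0.4 to −0.8; SD 21.9.
- CNC effect only: planned bias −0.2 to −3.6; after adding baseline CNC, −0.4 to +0.8, with the SD changed by about −7% to +6%.
- Change also falling 0.2 to 0.4 points per dB: planned bias −0.6 to −4.9; after adding both covariates, −0.6 to +1.7, usually at little cost in SD but up to about 24% when overlap is almost absent.
- Only 20 to 42% of subjects fall in quintiles with at least three from each trial.

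Further runs under similar ranges gave planned bias from +1.3 to −4.8 and sampling SDs of about 4 to 10. When CNC affected change only above 30% and the EAS CNC range was 0 to 60, the added terms raised the bias from about 0.7–0.8 to 1.0–1.2 points.

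**The case against.** The strongest reply is that the plan already adjusts for these variables through the propensity score, and that what is left is small beside sampling error. This largely stands. In simulation 1 the planned model removed about 87 to 94% of the raw bias. In further runs under ranges like those of simulation 2, adding covariates moved root mean square error by only about −7% to +9%.

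Second, a reader might infer that the entry rules make the two trials differ by design. The documents do not support that. Section 2.1 gives the approved EAS indication; the EAS trial's own criteria appear nowhere. Even on the stated words, the ranges can meet in the moderate band above 40 dB, and no CNC entry difference can be shown. Section 2.1 also cites a series of 22 subjects in which preoperative thresholds did not correlate with postoperative performance, so the low-frequency slope could be near zero. With that slope at zero and no CNC shift, the planned bias vanishes (last row of the table).

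Third, a linear covariate suits simulations built on linear effects, and the curved CNC case shows that it can slightly hurt. In a quintile with one trial there is nothing to compare directly, and the added terms can only extrapolate.

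Finally, section 10.9 sets no hypothesis or decision rule, and sections 10.1 and 10.4.1 leave further detail to a later SAP. That lowers the stakes. It also means the change can still be prespecified. A residual bias of this kind does not shrink with more subjects, so a near-free reduction is worth taking.

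**Conclusion.** The point holds as a cheap improvement to a supportive analysis. With only study and quintile in the outcome model, some imbalance in baseline CNC and low-frequency hearing probably remains within strata. With no true difference, the spurious difference is roughly 0 to 5 points, usually against the current trial, beside a sampling SD of about 3 to 10 points. These sizes rest on assumed EAS ranges and assumed slopes and are illustrative.

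Two stronger conclusions do not follow. The collected baseline values would reduce the bias; it cannot be said that they would remove it, because that depends on roughly linear effects and on real overlap. Nor does this threaten study success, which section 4.2.1 ties to the two co-primary endpoints alone.

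**What to change.** In section 10.9, or in the SAP before the final analysis:
- Keep the propensity quintile, entered as a five-level class.
- Add continuous baseline CNC score to the model for CNC change.
- Add low-frequency PTA as a second continuous covariate, or as a sensitivity analysis where few quintiles contain both trials.
- Report the number of subjects from each trial in each quintile, so that a reader can see how much of the estimate rests on direct comparison.
- Describe the study coefficient as an adjusted between-trial difference, since this is a one-arm trial with every subject treated and the coefficient contrasts two cohorts.

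The cost is a few lines of text and one or two model terms, with no new data. The downside is a somewhat wider interval from the low-frequency term when overlap is very poor (up to about 24% in the simulated extremes).

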#### 1 PURPOSE

The purpose of this investigation is to expand FDA-approved labeling for MED-EL cochlear implants to include adults who have moderate to profound sensorineural hearing loss and obtain limited benefit from appropriately fit hearing aids. Limited benefit from amplification is defined by test scores of 60% correct or less in the ear to be implanted (70% or less in the non-implanted ear) on monosyllabic words in quiet.

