#### 4.2 STUDY ENDPOINTS

#### 4.2.1 PRIMARY ENDPOINTS

The co-primary endpoint will be the comparison of CNC word score with the cochlear implant at six months post-activation to the pre-operative aided CNC word score in the implanted ear. Improvement will be defined as equal to or greater than 10 percentage points. Testing will occur in the soundfield at 60 dB SPL. The second co-primary endpoint will be the comparison of AzBio sentence score in noise with the cochlear implant at six months post-activation to the pre-operative aided AzBio score in the implanted ear. Improvement will be defined as equal to or greater then 10 percentage points. Testing will occur in the soundfield at 60 dB SPL with a signal-to-noise ratio of +10 dB SNR.

Study success will be determined based on the analysis of both co-primary endpoints. In order for the study to be considered successful, both co-primary endpoints must be met.

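### Does Section 10.9 need changing because its comparison with the EAS trial models CNC only and asks for no display of propensity-score overlap?

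*Combined protocol and SAP*

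**What the plan says.** Section 10.9 starts from the statement that "The primary endpoints of this trial were also measured in the Electric-Acoustic Stimulation clinical trial" and says this study's results will be compared with that trial. A logistic model on age, sex, baseline CNC and low-frequency hearing loss gives the propensity score. The two trials are pooled and "five strata will be formed using the quintiles of the scores". On the outcome it says "The analysis of CNC word score will be done using generalized linear models", with change in CNC as the dependent variable and study and quintile as predictors. AzBio is not named in the section, as outcome or as covariate.

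On overlap, the section says an analysis of this type "requires that there is good overlap of the propensity scores" from the two trials, and adds that "In the absence of good overlap, estimate of the treatment effect can still be made, but may be severely biased". It names no diagnostic, criterion or action.

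Elsewhere, Section 4.2.1 states that for success "both co-primary endpoints must be met", and Section 10.4.2 tests each by a one-sided paired t-test against 10 points. Section 10.1 says a SAP will be written before the final analysis, and Section 10.4.1 sends further method detail there. The revision history (version 1.1) lists the EAS comparison among changes recommended by FDA.

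**The concern.** Two things catch the eye.

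The first is endpoint scope. The opening sentence is plural, but the model covers one endpoint. Sections 10.4.8, 10.4.10 and 10.8 each name both scores, so the silence on AzBio could be an oversight. AzBio is required for success, and Section 10.5 says its planning values came from the EAS trial, so EAS data for it exist. It also has the lower stated power (83% against 90%) and the smaller planned gain over the margin (15 − 10 = 5 points against 24.4 − 10 = 14.4). If the choice stays open until the data are seen, an AzBio comparison could be shown or left out according to how it looks.

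The second is overlap. Section 5.1 requires a low-frequency pure-tone average (PTA) above 40 dB and sets no upper limit. Section 2.1 says that under the EAS approval "individuals with normal hearing to moderate hearing loss in the low frequencies qualify for cochlear implantation". Low-frequency loss is one of the propensity variables, so thin overlap is plausible. The label sought in Section 1 covers "adults who have moderate to profound sensorineural hearing loss and obtain limited benefit from appropriately fit hearing aids". Without counts by quintile, a reader could take the adjusted difference as describing that whole population when it may rest on a subset.

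**Working it through.** Section 10.9 contains no figure to reproduce. The check is a reading of the text, followed by an illustration of what thin overlap would do.

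**Endpoint scope.** The propensity variables include baseline CNC but not baseline AzBio, which fits a comparison meant for CNC. CNC-only wording is also not unique to this section: the per-protocol sentence in Section 10.4.5 and the list randomisation in Section 10.7 name CNC alone. The opening sentence reports what the EAS trial measured. The later sentences say what will be modelled, and an analyst following them fits one model, for CNC.

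**Coding of quintile.** Five strata formed from quintiles is ordinary language for a categorical factor. Nothing in the section suggests a numeric score.

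**What thin overlap does.** With quintile as a factor in an additive linear model, the study contrast is a weighted mean of within-quintile differences. The weight is w = n1·n0/(n1 + n0), where n1 and n0 are the counts from this trial and the EAS trial. A quintile holding one trial only has w = 0. The standard error is SD/√Σw.

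Inputs:
- n1 totals 50 (Section 4.1).
- SD is 21.9 (Section 10.5), used only to set the scale.
- The EAS size is not in the documents; 50 is assumed here.
- The shift in low-frequency hearing between trials is assumed to be 0 or 2 SD, with the other covariates alike.

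Mean simulated counts by quintile, and the weights they give:

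| Shift | This trial | EAS | w | Σw |
|---|---|---|---|---|
| 0 | 7.2, 8.9, 9.9, 11.1, 12.9 | 12.8, 11.1, 10.1, 8.9, 7.1 | 4.61, 4.94, 5.00, 4.94, 4.58 | 24.07 |
| 2 SD | 0.5, 3.1, 9.9, 17.0, 19.5 | 19.5, 16.9, 10.1, 3.0, 0.5 | 0.49, 2.62, 5.00, 2.55, 0.49 | 11.14 |

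- No shift: SE = 21.9/√24.07 = 4.5 points.
- 2 SD shift: SE = 21.9/√11.14 = 6.6 points (6.7 when averaged over the simulated datasets).
- In the shifted case the top quintile holds 19.5/50 = 39% of this trial's subjects and 0.49/11.14 = 4% of the weight.

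The SD is itself uncertain. With n = 50 and one-sided 0.025, an SD of change of 21.9 gives 99.5% power for CNC, not the stated 90%. An SD of 21.9 × √2 = 31.0 gives 89.7%. At 31.0 the two standard errors become 6.3 and 9.3. That discrepancy belongs to Section 10.5 and does not bear on this point.

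**How far the answer depends on assumptions.** A second simulation took 60 EAS subjects and four assumed pairs of PTA ranges, from 20–70 dB (EAS) against 41–80 dB (this trial) to 10–55 against 41–100 dB. The number of this trial's 50 subjects in quintiles with no EAS subject was:

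- PTA uniform in this trial: 0.3, 16.6, 22.1, 23.4.
- PTA skewed toward 41 dB: 0.0, 0.3, 13.6, 21.2.

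The share therefore runs from none to 23.4/50 = 47%, and the documents cannot narrow it.

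**What depends on the result.** Section 10.9 sets no hypothesis, no alpha and no decision rule. The tests in Section 10.4.2 use this trial's data only.

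**The case for a change.** The best case for a change is that this comparison was added for the regulator, and that the general deferral to a SAP does not guarantee that these items appear. Section 10.8 expressly sends its follow-up methods to the SAP; Section 10.9 does not. The remedy would be cheap: a sentence on AzBio, one on coding and one baseline table. All of that is fair, and the gap between the plural opening and the single model is real. It is a gap in description, though. Following the section as written gives a valid CNC comparison, with its main limitation already stated.

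One could also argue that AzBio would be the sharper contrast, since 8.4/21.9 = 0.38 of the CNC standard error. This does not stand. It compares raw points on two different tests. On a standardised scale the planned excess over the margin is 5/8.4 = 0.595 for AzBio and 14.4/21.9 = 0.658 for CNC. If the planning SDs are per-visit values, the ratio also requires equal pre–post correlations for the two tests.

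A last argument is that the section warns of the wrong thing, because the main loss under thin overlap is coverage and precision, with little bias. With quintile as a factor, simulated bias was small (−1.8 to +0.3 points), but under an assumed effect of PTA on the change score. Doubling the linear slope from −0.3 to −0.6 points per dB doubled the bias in the widest uniform-PTA setting, from about −1.1 to −2.2. The documents give no slope, so the plan's caution is not shown to be misplaced.

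**Conclusion.** No change follows. Section 10.9 leaves two details unsaid: whether AzBio is compared with the EAS trial, and how overlap will be shown. Both belong to a supportive analysis outside the success rule, the plan already states the overlap condition and the risk if it fails, and further detail is assigned to a SAP that is not among the documents. An analyst running a five-stratum propensity model will tabulate subjects by trial and stratum as a matter of course, and that table shows which subjects the estimate describes. AzBio is not hidden by the omission: its primary test and its individual listing (Section 10.4.10) are reported in any case.

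The possible loss of coverage runs from 0 to about 23 of 50 subjects, entirely on assumed EAS sizes and hearing ranges. Section 2.1 describes the approved EAS indication, not the EAS trial's own subjects. The conclusion would differ if the EAS comparison carried a decision rule or a claim of its own; nothing in the protocol gives it one.
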